Excipients: Lactose monohydrate 0.267 g, microcrystalline cellulose 0.03 g, magnesium stearate 0.003 g

Dosage: Per os. One tablet per intake (hold in mouth until complete dissolution – regardless of meal). The first 2 hours – every 30 minutes, then 3 additional doses with equal intervals. On days 2-5 – on tablet 3 times a day.

Dosage form: Orodispersible tablets

Description: Flat cylinder-shaped scored beveled edge white to off-white tablets

Storage conditions: Store at temperature below 25°C. Keep out of the reach of children.

Group 2

Name: Placebo

Active ingredient: NA

Excipients: Lactose monohydrate 0.267 g, microcrystalline cellulose 0.03 g, magnesium stearate 0.003 g

Dosage: Placebo using Anaferon for children scheme

Dosage form: Orodispersible tablets

Description: Flat cylinder-shaped scored beveled edge white to off-white tablets

Storage conditions: Store at temperature below 25°C. Keep out of the reach of children

Treatment period

Anaferon for children/Placebo treatment period is 5 days.

Observation period

Overall the subject is observed for 14 days (screening, randomization, treatment initiation – day 1, study therapy period – 5 days, follow-up – 1 day, phone visit – day 14).

Basic therapy

Throughout the study the subject may have symptomatic therapy of influenza/ARVI based on the accepted treatment standards including expectorants, mucolytics, vasoconstrictive nasal drops, where necessary – detoxifying therapy, as indicated* – approved antipyretics**, in case of bacterial complications of influenza/ARVI – antibacterial drugs except for antiviral, immunomodulating and other products specified in section “Prohibited concomitant therapy”.

* Indications for antipyretics products [11, 14, 34]:

Body temperature > 38.5°C;

Body temperature 38.0°C against concomitant chronic pulmonary, cardiac, nervous system diseases.

In case the antipyretic product was prescribed and given to the child by parents/adoptive parents on their own (without physician’s prescription) with no indications, the subject will not be withdrawn. Parents/adoptive parents should record temperature values in patient’s diary prior to the product administration, its name and dose.

** The products allowed as antipyretics (ATC group is specified in brackets):

1. Paracetamol (N02BE01).

2. Ibuprofen (M01AE01).

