3. Metamizole sodium (N02BB02) – on prescription only (for emergency assistance in case of hyperthermia uncontrolled by paracetamol/ibuprofen able, parenterally).

The product will be chosen by the investigator who will issue the antipyretic product to the subject at Visit 1.

[figure not shown]
Prohibited concomitant therapy

One month prior to enrollment as well as throughout the study (from signing patient information sheet (informed consent form) and screening initiation) the following products are not allowed (ATC group is specified in brackets):

1. Antiviral products (J05) except for Anaferon for children prescribed within the study.
2. Immune sera and immunoglobulins (J06).
3. Vaccines (J07).
4. Antitumour products (L01) and antitumour hormonal products (L02).
5. Immunostimulants (L03) including:
 - Colony-stimulating factors (L03AA) – filgrastim, molgramostim, lenograstim, pegfilgrastim.
 - Interferons (L03AB) – interferon-alpha, interferon-gamma, interferon alpha-2a, interferon alpha-2b, interferon alpha-n1, interferon beta-1a, interferon beta-1b, peginterferon alpha-2b, peginterferon alpha-2a.
 - Interleukins (L03AC) – aldesleukin.
 - Other immunostimulants (L03AX) – BCG-vaccine; pidotimod; glatiramer acetate.
 - Interferon inducers (including acridonacetic acid, meglumine acridonacetate, polyadenyl and polyuridyl acid complex, methylphenylthiomethyl-dimethylaninomethyl-hydroxybromindole carboxylic acid ethyl ether, oxodihydroacridinylacetate sodium, cagocel, tilorone).
 - Products containing thymus hormones (alpha- thymosin, alpha-glutamyl- tryptophane, thymus extract, thymoptin).
 - B-activin.
 - Synthetic immunostimulants (including levamisole, alpha-glutamyl- tryptophane).
 - Bacterial immunomodulators (including ribomuyil, sodium ribonucleate, deoxyribonucleate sodium, IRS-19, imudon, etc.).
6. Immunodepressants (L04).
7. Products for which allergic reactions have been recorded previously.
8. Products forbidden as antipyretic products:
 - Butylpyrazolidones (M01AA) including phenylbutazone.

- Acetic acid (M01AB) derivatives including indomethacin, diclofenac, ketorolac, aceclofenac.
- Oxicams (M01AC) including piroxicams, meloxicam, tenoxicam, lornoxicam.
- Propionic acid (M01AE) derivatives.
- Coxibs (M01AH).
- Niflumic acid (M01AX02).
- Acetylsalicylic acid (N02BA01) including in combination with other products.
- Pyrazolones (N02BB) including combinations with other products (except for metamizole sodium – on prescription).

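### Prohibited concomitant therapy, item 8, bans the whole M01AE class without excepting ibuprofen (M01AE01), which the same plan allows as an antipyretic

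*Combined protocol and SAP*

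**What the plan says.** **What is allowed.** The Basic therapy section opens with "Throughout the study the subject may have symptomatic therapy of influenza/ARVI" and lists three permitted antipyretics with their ATC codes: paracetamol (N02BE01), "Ibuprofen (M01AE01"), and metamizole sodium (N02BB02). Metamizole needs a prescription and is kept for emergencies in which paracetamol or ibuprofen has failed to control the fever. On supply, the section states: "The product will be chosen by the investigator who will issue the antipyretic product to the subject at Visit 1". If parents give an antipyretic on their own initiative and without indication, "the subject will not be withdrawn".

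**What is banned.** The Prohibited concomitant therapy section has a single lead-in that sets its period as "One month prior to enrollment as well as throughout the study". Item 8, headed "Products forbidden as antipyretic products", includes the line "Propionic acid (M01AE) derivatives", which carries no exception. The pyrazolone line (N02BB) in the same item does carry one: "except for metamizole sodium", on prescription.

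**What depends on the list.** Exclusion criterion 11 rules out a child who took any medicine in that section in the month before inclusion. Discontinuation criterion 6 covers ineligible children who were enrolled. The first exclusion from the Full Analysis Set (FAS) removes enrolled children who do not comply with the inclusion and exclusion criteria.

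**The concern.** One drug is both allowed and banned, and the ban feeds an eligibility criterion. The trial recruits children aged 3 to 12 with a temperature of at least 38.0°C within 24 hours of the first symptoms, and the first visit takes place at home. A parent may well have given ibuprofen for that fever before the physician arrives. A site that applies item 8 word for word would turn the child away. A site that relies on the allowed list would enrol the child.

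The wording also reaches the analysis sets. If a child were enrolled after home ibuprofen and later held to be ineligible on the letter of item 8, the plan's own rules would permit discontinuation and removal from the FAS. The trigger would be a drug that the plan treats as ordinary supportive care.

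**Working it through.** No figure in the plan is in dispute. The check is a comparison of texts.

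**Step 1: match each allowed antipyretic to the banned classes in item 8.**

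| Allowed antipyretic | ATC code | Banned class containing it | Exception written? |
|---|---|---|---|
| Paracetamol | N02BE01 | none | not needed |
| Ibuprofen | M01AE01 | M01AE | no |
| Metamizole sodium | N02BB02 | N02BB | yes, on prescription |

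The first five characters of M01AE01 are M01AE, so membership follows from the plan's own codes. Ibuprofen is the only one of the three that is both allowed and banned. The metamizole row shows how the item handles an allowed drug inside a banned class; the matching words for ibuprofen are absent.

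**Step 2: see whether other text gives the allowed list precedence.** It does not say so. The Study design section permits symptomatic therapy except for products in the Prohibited concomitant therapy section, and Basic therapy refers to the same section. Both cross-references lead back to the list that contains the unqualified line.

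**Step 3: see which period each text covers.** The ban covers the prior month and the study. The Basic therapy permission is worded for the study period. The rule on antipyretics given by parents concerns withdrawal, not eligibility. No sentence expressly exempts ibuprofen taken before enrolment.

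**Step 4: follow the literal reading.** Ibuprofen at home before Visit 1 is intake of a listed medicine within the month, so criterion 11 is met. If the child is screened out, the child never enters an analysis set. If the child is enrolled and later judged ineligible, discontinuation criterion 6 and the first FAS exclusion become available.

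**Step 5: size.** The documents give no rate of ibuprofen use before enrolment and do not say how sites would read item 8. The number of children affected therefore cannot be computed.

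**The case against.** The strongest reply is that the intent is plain. Ibuprofen is named individually with its own code, and a specific permission normally prevails over a general class line. It is named again in the condition for using metamizole. The investigator chooses and issues the antipyretic at the visit at which eligibility is assessed, so a literal reading would exclude a child for a drug that may be handed out at that same visit. Item 8 is headed as the counterpart of the allowed list. One lead-in governs both periods, so if item 8 means antipyretics other than the allowed ones, ibuprofen is outside it before enrolment as well as on study.

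Most of this stands. In particular, it would be inconsistent to read item 8 by its intent on study and by its letter in the prior month. The intended meaning is the same in both periods, and so is the literal one. What the reply does not remove is the wording: an operative eligibility rule says something other than what was meant, and no sentence resolves it.

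Three stronger readings are tempting, and the documents support none of them.

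- **That ibuprofen on study forces discontinuation** as a need for a product not allowed. The allowed list, the issue at Visit 1 and the metamizole condition all point the other way.
- **That the treatment comparison is biased or power is lost.** Use before enrolment is a baseline fact that precedes double-blind allocation, so no difference between arms is expected. Nothing in the documents quantifies a loss of subjects.
- **That sites were left with no guidance.** The document describes itself as a protocol summary. One can say that this text lacks the exception, not that every instruction given to sites lacked it.

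**Conclusion.** The point holds as a **minor** drafting error. Item 8 omits an exception for ibuprofen that the rest of the plan clearly intends. Read literally, it makes ibuprofen given at home before Visit 1 an exclusion under criterion 11, with possible removal of an enrolled child under discontinuation criterion 6 and the first FAS exclusion. Removal from the FAS would need three things in turn: ibuprofen in the prior month, enrolment, and a later literal ruling of ineligibility. Nothing in the documents shows that this sequence is likely.

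The size is not estimable, and no effect on bias, power or the planned number of subjects is claimed. The conclusion rests only on the ATC codes and wording printed in the plan. Confidence is high that the two lists clash in this text. How often sites would act on the literal reading is unknown.

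**What to change.** Extend the line "Propionic acid (M01AE) derivatives" in item 8 with the words *except ibuprofen (M01AE01)*, in the same manner as the metamizole exception. Nothing further is needed: the existing lead-in applies the exception to both the prior month and the study period, and exclusion criterion 11 follows because it refers to the same list. The discontinuation criteria and the analysis-set definitions need no change, and the metamizole restriction stays as it is.

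The cost is a one-line protocol correction and a short note to sites. Design, sample size and data collection are untouched.

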**International multicenter double-blind placebo-controlled
randomized parallel group clinical trial of efficacy of
Anaferon for children in the treatment of influenza and
acute respiratory viral infections in children**

Phase IV

Sponsor	OOO «NPF «MATERIA MEDICA HOLDING»
Protocol number	MMH-AD-004
Version date:	August 01, 2016
ClinicalTrials.gov Id:	NCT02072174

Protocol Summary

This document represents the protocol summary for the study on human subjects. The study will be carried out in accordance with ICH GCP, National Standard of the Russian Federation GOST 52379-2005 "Good Clinical Practice", Helsinki Declaration of World Medical Association, relevant requirements of the regulatory authorities as well as the study procedures.

Title of Study

International multicenter double-blind placebo-controlled randomized parallel group clinical trial of efficacy of Anaferon for children in the treatment of influenza and acute respiratory viral infections in children.

Phase: IV

Sponsor: OOO "NPF "Materia Medica Holding", Moscow, Russia

Protocol No. MMH-AD-004

Study purposes

- To obtain additional data on therapeutic efficacy of Anaferon for children in the treatment of influenza and acute respiratory viral infections (ARVI) in children.

Endpoints

Primary endpoint

1. Average illness duration (until recovery¹ or significant improvement²).

Secondary endpoints

1. Percentage of patients with recovery¹/improvement² in health on days 2, 3, 4 and 5 of observation treatment (according to the patient's diary), on days 3 and 5 of therapy (according to physician's objective examination).
2. Changes in fever (changes in temperature on days 2, 3, 4 and 5 of observation treatment).
3. Percentage of patients with normal body temperature ($\leq 37.0^{\circ}\text{C}$) on days 2, 3, 4 or 5 of observation treatment.
4. Severity of clinical manifestations of influenza/ARVI in scores on days 3 and 5 of observation treatment – according to physician's objective examination; on days 2-6 of observation – according to patient's diary.
5. Assessment of the Severity of Influenza Virus / ARVI Using the "Area Under the Curve" for an Overall Symptom Assessment (based on the results of area under curve for total

¹ **Recovery criteria:** temperature $\leq 37.0^{\circ}\text{C}$ + lack of symptoms within 24 hours.

² **Improvement criteria:** temperature $\leq 37.2^{\circ}\text{C}$ + total symptom score ≤ 2 .

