symptom score³ and nasal/throat/chest score on days 1, 3, 5 and 7 of observation – according to physician’s objective examination; on days 1-7 of observation – according to patient’s diary).

6. Number of intakes of antipyretic drugs according to indications on days 1, 2, 3, 4 and 5 of therapy.
7. Changes in viral load⁴ during the treatment and follow-up periods.
8. Percentage of patients with exacerbation of the disease course (complications requiring antibiotic drugs or hospitalization).

Safety assessment

- Presence and nature of adverse events during therapy, their relationship with the product and other characteristics.

Study design

Study design: multicenter double-blind placebo-controlled randomized parallel-group study.

The study will enroll outpatients of both genders aged 3-12 years with clinical signs of influenza/ARVI including fever $\geq 38.0^{\circ}\text{C}$ seeking for medical advice within the first day after the disease debut. The first visit shall be made at the subject’s home. After signing patient information sheet (informed consent form) by the parent/adoptive parent for the subject’s participation in the study his/her medical history will be collected, objective examination will be performed and concomitant therapy will be recorded. Nasal swab for rapid influenza diagnostics will be collected. In case of positive rapid test the physician will take nasal and oropharyngeal swabs (nasopharyngeal swab) for further PCR diagnosis of influenza A and/or B to determine the viral load. In case of negative result of rapid test the physician will take nasopharyngeal swab for further PCR to detect other respiratory viruses.

If the subject meets inclusion criteria and has no exclusion criteria at visit 1 (Day 1) he/she shall be enrolled and randomized into one of the two groups: group 1 will receive Anaferon for children for 5 days; group 2 – placebo according to Anaferon for children for 5 days. Parent/adoptive parent will receive a diary to record axillary temperature of the subject on a daily basis in the morning and evening (temperature is measured with a standard non-mercuric

³ **Total symptom score** is calculated based on intensity of each influenza symptom at subsequent statistical treatment by the experts of OOO “NPF “Materia Medica Holding”.

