14. Subjects whose parents/adoptive parents, according to the investigator's point of view, will not follow the observation requirements during the study or study product dosing regimen.
15. Participation in other clinical studies within 3 months prior to the inclusion in the study.
16. Parent/adoptive parent of the subject is related to the investigator team of medical facility directly involved in the study or is a close relative of the investigator. Close relatives include spouse, parents, children or brothers (sisters) regardless of whether they are biological or adoptive ones.
17. Parent/adoptive parent of the subject is working in OOO “NPF “Materia Medica Holding”, i.e. is the company official, temporary contract worker or an appointed official responsible for the study or their close relatives.

⁶ 1 alcohol unit – 0.33 L light beer/150 mL of unfortified wine, 40 mL of liquors.

Discontinuation criteria

1. Inability or refusal of the subject, his/her parents/adoptive parents to compliance the protocol.
2. Necessity in the medical products not allowed within the study.
3. Development of adverse event requiring the product discontinuation.
4. Subject's or parents'/adoptive parents' wish to terminate the study early due to lack of therapeutic efficacy or any other reason.
5. Cases not specified by the protocol when, according to the investigator, further subject's participation is dangerous.
6. Enrollment of ineligible subject.

Number of subjects

Signed informed consent form is supposed to be obtained from 972 subjects (of them 772 – in the Russian Federation, 100 – in Republic of Belarus and 100 – in Ukraine); this would allow to complete all protocol procedures by at least 508 subjects (n=254 in Anaferon for children and Placebo groups).

Interim analysis

An interim statistical analysis is scheduled within the study. The interim analysis will be based on the findings from examinations and therapy of the protocol-set number of subjects who completed the study. Based on the proposed effect, the minimum required Per Protocol (PP) sample size will be 254 subjects (n=127 in Anaferon for children and Placebo groups).

Treatment

Group 1

Name: Anaferon for children

Active ingredient: affinity purified antibodies to human interferon-gamma – 0.003 g*

** applied to lactose monohydrate as water-alcohol mixture containing no more than 10^{-16} ng/g of the active form of the active ingredient*

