Study design scheme

Schedule of study procedures

Procedure/Visit	Visit 1 (Day 1)	Visit 2 (Day 3)	Visit 3 (Day 5)	Visit 4 (Day 7)	Visit 5 (Day 14±1)
Obtaining signed informed consent form (ICF)	+				
Collection of complaints	+	+	+	+	
Collection of medical history	+				
Objective examination	+	+	+	+	
Recording influenza/ARVI symptoms	+	+	+	+	
Inclusion/exclusion criteria assessment	+				
Recording concomitant therapy	+	+	+	+	
Rapid test for influenza viruses in nasal swabs	+				
Obtaining nasal and oropharyngeal	+	+	+	+	

swabs for PCR diagnosis of influenza (in case of positive result of rapid test for influenza)					
Obtaining nasal and oropharyngeal swabs for PCR diagnosis of other respiratory viruses (in case of negative result of rapid test for influenza)	+				
Randomization and prescription of the study therapy	+				
Issue of the study product	+				
Issue of antipyretic product	+				
Accounting and return of the study product, determination of compliance				+	
Issue of patient's diary	+				
Revision of correctness of diary filling		+	+	+	
Diary return				+	
Therapy safety assessment		+	+	+	+
Phone contact					+

Statistical Analyses

Samples

Statistical analysis will be carried out in the following sets:

Total set – all enrolled subjects whose parents/adoptive parents had signed ICF. This set will take into account all adverse events and related conditions during the study including prior to the study therapy initiation.

Total set of the subjects receiving at least one dose of the study product will be used for safety and tolerability analysis (Safety population), as all adverse events recorded in the subject after administration of the product will be taken into account.

Full Analysis Set. This set includes all enrolled subjects excluding those having at least one of the following events:

- 1) non-compliance with inclusion/exclusion criteria;
- 2) the subject did not receive a single dose of the study product;
- 3) lack of any data on the subject after prescription of the study product

This set most fully conforming to Intention-to-treat principle will be used for Intention-to-treat analysis (ITT-analysis) of the study product efficacy.

Per Protocol set. This set includes all subjects receiving per protocol therapy in full, completing all scheduled visits and having no major deviations from the protocol. This set will be used for Per Protocol analysis (PP-analysis) of the study therapy efficacy.

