Last Observation Carried Forward (LOCF) will be used for filling missing values.

Evaluation of sample size

Evaluation of sample size was based on the following rules and assumptions:

1. Statistical provisions.
 - 1.1 Power of statistical criteria " $P = (1 - \beta)$ " is considered to be equal to 80% (probability of correct rejection of null hypothesis is 0.8).
 - 1.2 Probability of error of the first kind " α " is admitted to be $< 5\%$ (probability of erroneous acceptance of alternative hypothesis is < 0.05).
 - 1.3 The statistical criteria used are two-sided.
 - 1.4 Calculation of total sample size was based on the assumptions on expected effects on primary endpoint claimed in the protocol.
 - 1.5 Effect of interim statistical analyses on probability of error of the first kind is regulated at each point (interim analysis, final analysis) using O'Brien-Fleming boundary.

2. Assumptions on expected clinical study effects.

It is assumed that the difference between average disease duration (until recovery or significant improvement) in Anaferon for children and Placebo groups will be less than 0.5 days, while standard deviation in both groups will not exceed 2 days.

Taking into account that statistical analysis will be performed twice – at interim analysis and at final analysis – based on the assumed effect the minimum required size of each group (product and placebo) will be as follows:

Number of subjects	Interim analysis	Final analysis
Number of subjects in both groups	254	508
including		
- number of subjects in Anaferon group	127	254
- number of subjects in Placebo group	127	254

Given withdrawal at screening, including due to negative rapid influenza test (the ratio is 1 subject with positive test/5-6 subjects with influenza-like symptoms and negative influenza test) and during the study, the final sample size will be 972 subjects to be enrolled.

This calculation is made using the formula: $N_T = N_{PP} / (1 - C_w)$, where N_T – final sample size; N_{PP} – scheduled number of subjects completing the study per protocol ($N_{PP}=508$); C_w – withdrawal coefficient ($C_w=0.4774$).

Interim analysis

Interim analysis of *Particular Per Protocol (pPP)* is scheduled within the study.

Purposes of interim analysis:

- Ability to adjust sample size in case in minor deviation of the effect achieved from the effect specified at baseline;

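### In the Full Analysis Set, the unrestricted LOCF rule carries early-illness temperatures, scores and antipyretic counts into later days of secondary endpoints 2-6 for children who leave, or stop the diary, while still ill

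*Combined protocol and SAP*

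**What the plan says.** All references are to the combined protocol and SAP.

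- **Missing values.** The text closing the Samples part of Statistical Analyses reads: "Last Observation Carried Forward (LOCF) will be used for filling missing values". It is not limited to any endpoint, analysis set or reason for missingness. No other method and no sensitivity analysis is named.
- **Endpoints (Secondary endpoints, items 2-6).** Item 2: "changes in temperature on days 2, 3, 4 and 5 of observation treatment". Item 3: "Percentage of patients with normal body temperature", assessed "on days 2, 3, 4 or 5 of observation treatment". Item 4: "Severity of clinical manifestations of influenza/ARVI in scores on days 3 and 5 of observation treatment" by physician, and on Days 2-6 by diary. Item 5 is an area under the symptom-score curve to Day 7. Item 6: "Number of intakes of antipyretic drugs according to indications on days 1, 2, 3, 4 and 5 of therapy".
- **Who is analysed (Samples).** The Full Analysis Set, used for the ITT efficacy analysis, drops only ineligible children, those never dosed, and those with "lack of any data on the subject after prescription of the study product". The Per Protocol set requires every scheduled visit.
- **Leaving early (Discontinuation criteria, item 4).** Families may leave on a "wish to terminate the study early due to lack of therapeutic efficacy or any other reason".
- **State at entry (Inclusion criteria, items 2-3).** Every child has a temperature of 38.0°C or more and is within 24 hours of onset.

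**The concern.** LOCF assumes that a child's state stays fixed at the last record. Here every child starts febrile, and the endpoints exist to follow resolution over a few days. A value carried from an ill day is therefore likely to be far from the value on the day it stands in for. For item 6 the difficulty is sharper: a count of events on one day is not a state that persists. A child with three recorded intakes on Day 3 who then leaves is scored three on Day 4 and three on Day 5, which is six intakes with no record behind them. If that child's last temperature was 38.2°C, the child also counts as not normal on Days 4 and 5, and the last symptom score is integrated to Day 7 in the AUC.

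Two consequences follow. Late-day means and variances rise in both arms, which costs precision. And if the arms lose children at different rates, for whatever reason, that difference is converted into an apparent difference in fever, symptoms and antipyretic use.

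**Working it through.** **The plan's own figures, for context.** With a difference of 0.5 days, SD 2, two-sided alpha 0.05 and power 80%: n = 2 × (1.96 + 0.8416)² × 2² / 0.5² = 251.2, so 252 per arm. The two-look O'Brien-Fleming factor of 1.0078 gives 253.1, so 254 per arm as stated. Enrolment is 508 / (1 − 0.4774) = 972.06, against 972 stated. These figures reproduce and are not in dispute; 254 per arm is used below.

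**Inputs the documents do not give.** The withdrawal coefficient 0.4774 combines screening loss with in-study loss, so it cannot serve as a post-randomisation dropout rate. The following are assumptions:

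- mean daily intakes of 2.0, 1.2, 0.6, 0.25 and 0.1 on Days 1-5, Poisson with gamma frailty (shape 2, mean 1), so that variance = m + m²/2 and E[X²] = m + 1.5m²;
- a proportion d of each arm leaves, independently of outcome;
- pattern A: last observed day is Day 2, 3 or 4 for 50%, 30% and 20% of leavers;
- pattern B: last observed day is Day 3 or 4 only, for 60% and 40%.

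**Day 5 mean under LOCF** = (1 − d) × 0.10 + d × (mean carried value).

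- Carried mean, A: 0.5 × 1.2 + 0.3 × 0.6 + 0.2 × 0.25 = 0.83.
- Carried mean, B: 0.6 × 0.6 + 0.4 × 0.25 = 0.46.

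**Day 5 variance under LOCF** = (1 − d) × 0.115 + d × (carried E[X²]) − mean². The true value is 0.1 + 0.1²/2 = 0.105.

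- Carried E[X²], A: 0.5 × 3.36 + 0.3 × 1.14 + 0.2 × 0.344 = 2.091.
- Carried E[X²], B: 0.6 × 1.14 + 0.4 × 0.344 = 0.8215.

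| Dropout | Mean, A | Variance, A (ratio to 0.105) | Mean, B | Variance, B |
|---|---|---|---|---|
| 5% | 0.137 | 0.195 (1.9) | 0.118 | 0.136 |
| 10% | 0.173 | 0.283 (2.7) | 0.136 | 0.167 |
| 15% | 0.210 | 0.367 (3.5) | 0.154 | 0.197 |

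**Unequal dropout, 5% versus 10%, no drug effect.** z = gap / √((V₁ + V₂)/254), and rejection = Φ(−1.96 + z) + Φ(−1.96 − z).

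- A: gap 0.0365, standard error √(0.478/254) = 0.0434, z = 0.84, rejection 13.4%.
- B: gap 0.018, standard error √(0.304/254) = 0.0346, z = 0.52, rejection 8.2%.

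Simulations of several thousand trials per scenario agree:

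| Day 5 intakes, LOCF | t-test | Mann-Whitney |
|---|---|---|
| 5% vs 10%, pattern A | 12-13% | about 10.5% |
| 5% vs 10%, pattern B | 7-8% | about 7% |
| 3% vs 6%, pattern A | 8-9% | about 7% |
| 3% vs 6%, pattern B | about 6% | 5-6% |
| equal dropout | about 5% | about 5% |

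The t-test on observed counts alone, 5% versus 10%, rejects about 5%. That comparator is nominal partly because dropout was generated independently of outcome.

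**Normal temperature on Day 5.** Assume 30%, 55%, 75% and 88% normal on Days 2-5. Under pattern A a leaver carries 0.5 × 0.30 + 0.3 × 0.55 + 0.2 × 0.75 = 46.5%. At 5% dropout the arm shows 0.95 × 88 + 0.05 × 46.5 = 85.9%; at 10%, 0.90 × 88 + 0.10 × 46.5 = 83.9%. The false gap is 2.1 points, with rejection of about 10%. Under pattern B the carried figure is 63%, the arms show 86.8% and 85.5%, the gap is 1.25 points and rejection is about 7%.

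**The case against.** The strongest objections limit the point without removing it.

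- **Day 2 leavers may not be analysed.** In the Schedule of study procedures the first post-baseline visit is Day 3 and the diary is returned only on Day 7. No early-termination visit or diary retrieval is described. A child lost on Day 2 may have no post-prescription data and so fall outside the Full Analysis Set. This stands, and it is why pattern B is shown; pattern A holds only if those diaries are recovered.
- **The t-test may not be the test used.** Statistical criteria sends non-normal continuous variables to Mann-Whitney, and counts with a mean near 0.1 would not pass. This stands; the inflation is smaller but does not vanish.
- **Type I inflation needs unequal dropout.** The documents give no reason to expect a twofold difference in a blinded five-day treatment. A reader might infer that permitted withdrawal for lack of efficacy itself produces a false effect when the drug does nothing. It does not: withdrawal for that reason that truly differs by arm implies some arm effect. Under the null, imbalance must come from other causes or chance.
- **The scope is limited.** Early leavers are not in the Per Protocol set, on which the sample size and interim analysis rest. The documents do not say which set is primary.
- **A reader might infer that LOCF scores doses never taken.** The documents support only doses never recorded, since families are issued an antipyretic and may have used it after leaving.
- **Direction is not fixed.** A child who leaves after fever resolves carries normal values.
- **Observed-data models are not immune.** Informative withdrawal could bias them too, and this was not simulated.

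**Conclusion.** The concern holds for the Full Analysis Set analysis of secondary endpoints 2-6. As written, the rule assigns early-illness values to later days for children who leave, or stop the diary, while ill. That is a defect in the stated method, not merely a missing detail.

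Its size depends on assumed intake and dropout rates. Late-day means and variances rise even with equal dropout: under pattern A, 5% dropout nearly doubles the Day 5 variance of intakes. Type I error is then unaffected. With 5% versus 10% dropout it is about 7-8% (Day 3/4 leavers only) to 12-13% (half leaving after Day 2, diaries recovered) by t-test, and about 7-10% by Mann-Whitney.

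The Per Protocol analysis is affected only by isolated diary gaps. Nothing here bears on the primary endpoint or the sample size. The change should be made, at the level of a secondary-endpoint correction.

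**What to change.** Remove LOCF as the main method for endpoints 2-6 and analyse observed daily values without imputation:

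- **Temperature and symptom scores (items 2, 4, 5):** a likelihood-based repeated-measures mixed model with arm, day and arm-by-day. Read day-specific contrasts from it, and derive the AUC contrast from the fitted day means by trapezoid weights.
- **Normal temperature (item 3):** a repeated-measures logistic model.
- **Antipyretic intakes (item 6):** a count model on observed days, for example negative binomial with observed days as exposure.
- **Fallback:** name in advance a simpler observed-data comparison in case sparse late-day data prevent convergence.
- **Sensitivity:** keep LOCF as a sensitivity analysis only.

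The cost is SAP wording and some programming. Statistical criteria already lists GENMOD and GLIMMIX, and no new data are needed. The downside is reliance on missing-at-random, which informative withdrawal could violate.
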